2. STUDY SUMMARY

Title of study	The Impact of continuous haemofiltration with high volume fluid exchange during cardiopulmonary bypass surgery on the recovery of patients with impaired renal function - A pilot randomised study
Lay title	Impact of blood purification devices on well-being of patients with moderately impaired kidney function and undergoing cardiac surgery
Study design	Single-centre, randomised, prospective clinical trial
No of subjects	60
Study timelines	
Planning, ethics and start-up Mar 2010 – Oct 2010
 
Recruitment Nov 2011 – Mar 2012
 
End of follow-up Mar 2012
 
Analysis and reporting Mar 2012
 
Final report May 2012

Inclusion criteria	Consenting men and women must be at least 18 years old, high-risk patients elective for on-pump coronary artery bypass graft surgery (CABG). They must also have impaired renal function established preoperative by an <60 ml/min measured within 4 weeks before surgery.
Exclusion Criteria	Patients undergoing surgery on the great vessels (aortic surgery) or valve surgery, have significant impaired liver function (serum bilirubin >60 or INR>2 without anticoagulation), patients who are further down the line of renal failure or on-dialysis, have malignancy and those that are pregnant.
Primary outcome measure	Incidents of ICU stay >3 days for patients with renal impairment identified as an estimated glomerular filtration (eGFR) <60 ml/min.
Secondary outcome measures	
Clinical
 
 1. Composite of perioperative incidences: Bleeding, sepsis, death, arrhythmias, stroke, and myocardial infarction 2. Need for postoperative continuous veno-venous haemofiltration (CVVH) in the ICU- Indications for requirement of postoperative continuous veno-venous haemofiltration must adhere to our surgical guidelines. 3. Mechanical ventilation time 4. Hospital stay 5. eGFR at 6 weeks follow-up 
Secondary Economic Outcomes: Resource utilisation associated with each of the two pilot arms such as: ICU stay and hospital stay, mechanical ventilation, medications, tests and procedures undertaken until the end of the follow-up period.

Follow-up	Outcome measures will be assessed until hospital discharge or 28 days, whichever is sooner and at 6 weeks follow-up appointment
-----------	---

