12. STUDY COMPLIANCE

We do not anticipate any problems with compliance because the treatment will be administered in theatre whilst the patient is under anaesthesia. Once consent is obtained before the operation the patients will not know what treatment allocation they have been

given when they wake up after the operation. There is also no evidence to suggest that patients will be lost during the in-hospital follow-up period or at their routine 6 weeks postoperative follow-up visit.

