15. FOLLOW UP DATA COLLECTION

1. Follow-up will be during the in-hospital stay phase and at 6 weeks post-discharge follow-up visit.
2. All information will be collected in structured Case Record Forms (CRFs).
3. A Manual of Operation documents containing relevant procedural instructions and definitions will be produced.
4. Data will be entered into a secure password protected database.
5. Prospective monitoring of adverse and clinical events will start at randomisation and will continue until hospital discharge
6. Costs associated with each of the two pilot arms, postoperative renal replacement therapy, ICU stay and hospital ward stay, and medications will be estimated up until hospital discharge.

7. Prospective monitoring of serious adverse and clinical events will start at randomisation and will continue until hospital discharge.

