17. SAFETY REPORTING

The study procedures adapted here are part of normal clinical practice. Safety will be assessed by tracking the number and percentage of adverse events (AEs) up to discharge from hospital. Serious and other adverse events will be recorded and reported in accordance with the International Conference for Harmonisation of Good Clinical Practice (ICH GCP) guidelines/the European Clinical Trials Directive 2001/20/EC and the Sponsor's Research Related Adverse Event Reporting Policy. ICH GCP requires that both investigators and sponsors follow specific procedures when reporting adverse/reactions in clinical trials. All serious adverse events **must** be reported to the steering committee and documented in CRFs. Such events result in death or are life-threatening, require hospitalisation or prolongation of existing hospitalisation, result in persistent or significant disability or incapacity or may have created a congenital anomaly or birth defect

Examples would include, but are not limited to:

- **Deaths related or unrelated to healthcare-acquired infection**
- **Life-threatening bleeding**
- **Intracranial haemorrhage**
- **Cerebrovascular accident**
- **Profound thrombocytopenia (platelet counts $\leq 50,000/\text{mm}^3$)**
- Allergic reactions

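### Event and safety monitoring stops at hospital discharge, a window the treatment is meant to shorten; the follow-up windows contradict each other, and the timetable leaves no room for the last patients' 6-week visits

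*Protocol*

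**What the plan says.** Four windows are stated, and they do not agree.

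- **Outcomes.** Section 2 (Follow-up row): "Outcome measures will be assessed until hospital discharge or 28 days, whichever is sooner and at 6 weeks follow-up appointment". The 28-day limit appears nowhere else.
- **Events and safety.** Section 15, item 5: "Prospective monitoring of adverse and clinical events will start at randomisation and will continue until hospital discharge". Item 7 repeats this for serious adverse events. Section 17: "Safety will be assessed by tracking the number and percentage of adverse events (AEs) up to discharge from hospital".
- **Resource use.** Section 2 counts "medications, tests and procedures undertaken until the end of the follow-up period". Sections 14 and 15 estimate costs only to hospital discharge.
- **The 6-week visit**, at which eGFR and EQ-5D are taken. Section 12 expects no losses "at their routine 6 weeks postoperative follow-up visit". Section 15, item 1, says: "Follow-up will be during the in-hospital stay phase and at 6 weeks post-discharge follow-up visit".

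On dates, Section 2 plans recruitment from November 2011 to March 2012, "End of follow-up Mar 2012", analysis in March 2012 and the final report in May 2012.

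The last paragraph of Section 5.1 hypothesises that haemofiltration reduces ICU stay, perioperative complications and overall hospital stay.

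**The concern.** An event window that closes at discharge has a length that is itself an outcome. If haemofiltration shortens stay, treated patients have fewer days in which a stroke, sepsis, arrhythmia or death can be counted, even if their daily risk is the same. A death at home or a readmission the week after discharge is outside the window in both arms. Yet death is a component of the composite, and Section 17 lists events requiring hospitalisation among those that are serious.

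The same dependence reaches the 6-week measurements if the visit is timed from discharge: eGFR and EQ-5D would then be taken at a postoperative day that depends on length of stay. A 28-day limit, if applied to hospital stay, would cut off the longest stays.

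This matters for a pilot because one stated aim (Section 4) is to judge whether the outcome measures are suitable and reliable, and another (Section 7.3) is to test the resource-use data collection. Windows that are unequal or undefined weaken both aims and could be carried into the definitive trial.

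**Working it through.** The plan gives no figure on this point to reproduce. (The 1112 patients in Section 13 size the definitive trial and are not in question here.)

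**1. The windows side by side**

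| Item | One place | Another place |
|---|---|---|
| Outcomes and events | Earlier of discharge and 28 days, plus 6 weeks (Section 2) | Randomisation to discharge, no cap (Sections 15, 17) |
| Resource use and costs | End of follow-up (Section 2) | Discharge (Sections 14, 15) |
| 6-week visit | From operation (Section 12) | From discharge (Section 15) |

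Section 2 could be read as reassessing every outcome at 6 weeks. However, Section 15 ends clinical-event monitoring at discharge, and the only measurements explicitly placed at 6 weeks are eGFR and EQ-5D.

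**2. The two visit anchors.** The postoperative visit falls on day 42. The post-discharge visit falls on day 42 + length of stay. With an assumed stay of 5 to 14 days (the protocol gives none), that is day 47 to 56.

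**3. The timetable.** Randomisation is on the day of surgery (Section 7), so recruitment dates are operation dates.

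- Recruitment from 1 November 2011 to 31 March 2012: 30 + 31 + 31 + 29 + 31 = 152 days.
- Last operation with a day-42 visit by 31 March 2012: 31 March − 42 days = 18 February 2012.
- Patient operated on 1 March: due 12 April 2012. Patient operated on 31 March: due 12 May 2012.
- Share due after the stated end, with uniform recruitment: 42/152 = 27.6%, and 60 × 0.276 = 16.6, about 17 of 60.
- Section 13's rate of 10 a month gives 50 patients in these five months: 50 × 42/152 = 13.8. The share is the same.
- Post-discharge anchor, assumed stay of 7 to 10 days: 49/152 = 32% to 52/152 = 34%, or 19 to 21 of 60.

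**4. The unequal window.** The protocol gives no length of stay, event rate or timing of events, so the size cannot be derived. The following figures are illustrations only, all with no true effect on event risk.

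- Constant daily hazard, control stay 10 days, treated stay 7 to 9 days: apparent treated rate = 1 − (1 − control rate)^(treated stay/10).
  - Control rate 30%: 1 − 0.70^0.9 = 27.5% to 1 − 0.70^0.7 = 22.1%.
  - Control rate 20%: 1 − 0.80^0.9 = 18.2% to 1 − 0.80^0.7 = 14.5%.
- Stay 2 days shorter, with a risk of 0.5 to 1% per day around discharge: 2 × 0.5 to 2 × 1 = 1 to 2 points.

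Many perioperative events occur early, so the constant-hazard figures are probably near the upper end.

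**The case against.** The strongest reply is that this is a feasibility pilot with a perioperative composite, for which an in-hospital window is natural. The primary outcome is settled well before discharge, CVVH is defined as occurring in the ICU, and ventilation time is in-hospital. This stands, and it limits the point to the composite, safety, hospital stay, resource use and the 6-week measures. With about 30 patients per arm, a window effect would also be small against chance: at an assumed 25% event rate, the standard error of the difference is √(2 × 0.25 × 0.75/30) = 11 points.

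A reader might infer four stronger things that the protocol does not support.

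- *That everything is counted only to discharge.* The summary adds a 6-week assessment, eGFR and EQ-5D are taken then, and Section 2 runs resource use to the end of follow-up. For costs the fault is a contradiction.
- *That the comparisons are biased by a known amount.* Every figure in step 4 above rests on assumed inputs.
- *That lower cost from a shorter stay is bias.* Fewer bed-days are part of the hypothesised benefit. Only uncounted use after discharge could distort the comparison.
- *That a quarter of the 6-week data will be missing.* Nothing says that visits due after March 2012 would be dropped. The dates are month-level and inconsistent elsewhere: start-up ends in October 2010 but recruitment starts in November 2011, Section 5.3 targets the financial year 2010-2011, and Sections 4, 5.3 and 13 plan six months' recruitment, not five.

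Nor does the protocol show how many stays exceed 28 days, or say outright that the cap applies to recorded length of stay.

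**Conclusion.** The point holds, with limits.

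What is certain from the text is that monitoring of clinical events, AEs and SAEs ends at discharge although a shorter stay is hypothesised; that the 28-day cap, the resource-use window and the visit anchor are each stated inconsistently; and that a March 2012 end of follow-up cannot hold the 6-week visit of anyone operated on after 18 February 2012. The 28% (about 17 of 60) assumes uniform recruitment of all 60 from 1 November to 31 March and the postoperative anchor. It is larger with the discharge anchor.

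What is conditional is the bias. The composite and safety comparisons can favour the arm discharged earlier, if stay differs and if events occur around or after discharge. Its size is unknown. The primary outcome is essentially unaffected, so this is a fault in the secondary outcomes and the follow-up schedule, worth correcting because the remedy is cheap.

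**What to change.** - Count the composite, serious adverse events (including death and readmission) and resource use in both arms over one fixed window, from surgery to 6 weeks after surgery, collected at the existing visit and from hospital records. State this identically in Sections 2, 14, 15 and 17.
- Record hospital stay without the 28-day cap.
- Anchor the 6-week eGFR and EQ-5D visit to the date of surgery in Sections 2, 12, 14 and 15.
- Set the end of follow-up to at least 6 weeks after the last operation, about mid-May 2012 on the stated dates (12 May for an operation on 31 March), and move the analysis and the May 2012 final report accordingly.

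The cost is wording, a few extra CRF items at a visit already planned, and reporting about 6 weeks later. Treatment does not change.

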3. FLOW DIAGRAM

4. RESEARCH OBJECTIVES

There is a widespread variability in clinical practice within cardiac surgery units worldwide on the use of haemofiltration on a case-by-case basis, the impact and safety of this modality however, is unknown. In addition, no evidence exists to suggest that haemofiltration as applied to patients during the period of the operation may have an impact upon the postoperative cost of care and clinical renal impairment outcomes. We hypothesise that the initiation of intraoperative haemofiltration with high-volume fluids exchange during cardiopulmonary bypass in patients with impaired renal function effectively reduces overall length of intensive care unit (ICU) stay and progression of renal impairment. Since no large randomised trial has undertaken this kind of study before, the design of the study is limited by the absence of past trial data that could be used as a reference. In order to overcome these limitations we propose to at first conduct a pilot feasibility study with the following objectives:

1. To assess the feasibility of randomising 60 patients with impaired kidney function (eGFR<60 ml/min) undergoing coronary artery bypass surgery in 6 months within a single-centre for intraoperative haemofiltration i.e. to investigate the likely recruitment rates and issues that may impact recruitment into the study.
2. To assess the suitability and reliability of the outcome measures.
3. To investigate the likelihood of recruitment into the main definitive study and explore issues that may impact recruitment such as staff requirements, barriers to recruitment, suitability and reliability of the outcome measures selected.

5. BACKGROUND

5.1 *INTRAOPERATIVE HAEMOFILTRATION*

Cardiac surgery can be associated with dysfunction of major organs [1]. The perioperative complications in patients with impaired renal function undergoing cardiac surgery increase hospital stay, mortality and eventually cost of healthcare [2]. It is estimated that up to 20% of patients undergoing cardiac surgery already have a pre-existing renal insufficiency (increased creatinine >132 µmol/L). An increasing body of evidence suggests that inflammatory factors and oxidant stress have significant roles in the pathogenesis of cardiovascular disease [3]. Indeed, increased production of reactive oxygen species (ROS) in the failing heart is a characteristic feature of oxidant stress. Patients with associated renal

disease have a strikingly increased oxidative stress and an impaired antioxidation system. It seems reasonable to expect that patients with renal impairment and elevated oxidative stress are at increased risk of complications after cardiac surgery [4]). According to the literature, postoperative development of acute renal failure (ARF) has adverse prognostic significance and itself increases the risk of death [5, 6]. Some of the other factors that contribute to poor outcome in these patients postoperatively are advanced age, preoperative left ventricular dysfunction, perioperative low cardiac output, duration of cardiopulmonary bypass (CPB) and aortic cross clamp time [7]. Activation of the inflammatory cascade is thought to account for some of the respiratory dysfunction and results in prolonged mechanical ventilation. In addition, a systemic inflammatory response induced by CPB may necessitate the use of intra-aortic balloon pump, the continuous administration of inotropic drugs, and at times extracorporeal life support. Mortality has remained high despite the use of different renal replacement therapies in these patients in the post-operative phase and after hospital discharge [8].

There are several potential explanations for such a high morbidity and mortality. It has been suggested that oxidative stress induced by cardiac surgery is involved in the pathogenesis of an underlying systemic inflammatory response (SIRS) experienced by most patient's perioperatively [9, 10]. This leads to a further reduction in antioxidant capacity and an increased onset of a cascade of events such as protein modification, lipid peroxidation, and the activation of circulating blood leukocytes. Some studies have also suggested transient endotoxemia as a major stimulus for the development of SIRS in these patients [11-13]. However, the pathogenesis involved in this phenomenon is not entirely clear. The association between perioperative renal impairment and mortality has been shown in several retrospective studies [14-17].

A recent randomised study demonstrated that both intraoperative haemofiltration and steroids attenuate the inflammatory response but only haemofiltration reduced time to tracheal extubation for adults after cardiopulmonary bypass [17]. In addition, another non-randomised study [18] demonstrated that haemofiltration during CPB attenuates postoperative anaemia, thrombocytopenia and hypoalbuminemia, may reduce post-operative bleeding and appears to decrease post-operative pulmonary complications. Also others [19] showed that the combined use of balanced ultrafiltration and modified ultrafiltration can effectively concentrate the blood, modify the increase of some harmful inflammatory mediators, and attenuate lung oedema and inflammatory pulmonary injury that

mitigates the impairment of pulmonary function. In view of the evidence that has shown that the use of haemofiltration during cardiopulmonary bypass reduces time to tracheal extubation, length of mechanical ventilation and attenuates postoperative anaemia, thrombocytopenia, hypoalbuminemia, post-operative bleeding and post-operative pulmonary complications, we hypothesise that this would be the basis for a reduction in ICU stay, perioperative complications and overall length of hospital stay, hence the objective of this proposal.

5.2 SEARCH FOR EVIDENCE

A review of current trials registered in the ISRCTN Register, NHS Trusts Clinical Trials Register, MRC UK and National Institutes of Health (NIH) randomised trial records held on NIH ClinicalTrials.gov website yielded no present or past randomised trials of this nature. In addition, we conducted an extensive literature search of the MEDLINE and EMBASE electronic databases between 1990 and July 2009. Terms that were used for the search were "haemofiltration", and "intraoperative ultrafiltration". The searches were limited to "human" and "English language". Reference lists of identified articles were scanned for additional potentially relevant publications in the Web of Science version 4.1.1, Institute for Scientific Information 2000 which identified all articles that cited the index publication. We were able to identify a number of previous studies that have investigated the impact of haemofiltration and demonstrated that it removes significant amounts of inflammatory mediators [15, 20, and 21]. In addition, others have demonstrated retrospectively the benefits of haemofiltration on patient's survival [14-16, and 22]. Unfortunately these studies were all retrospective and there is no indication as to the length and why haemofiltration was given to patients. In addition, no randomised trial has yet been conducted to establish the efficacy, safety and cost-effectiveness of haemofiltration as applied intraoperatively. We therefore propose for the first time to conduct a pilot randomised clinical trial that will evaluate the efficacy in terms of the reduction in duration of ICU stay for patient with significant preoperative renal impairment (**eGFR<60 ml/min**), removal of potentially harmful organ-damaging toxins, improvement in renal outcomes, projected health economics outcomes and safety of the procedure.

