13. PROPOSED SAMPLE SIZE

Calculation of an accurate samples size at this stage would not be precise since this is a pilot feasibility study. However, existing data accrued from our audit department suggest that, at the Liverpool Heart & Chest Hospital, incident rates for intensive care unit (ICU) stay >3 days for patients with estimated GFR <60 ml/min after isolated coronary artery bypass graft (CABG) surgery in years between 2002 and 2008 were 18%. We estimate that even if the proportion of these patients that stay in ICU for > 3 days is reduced to at least a mean of 12% because of intraoperative haemofiltration, this will be of significant clinical and economic benefit to the NHS. We have estimated that at 80% power (2-sided $\alpha=0.05$), 1112 patients with GFR <60 ml/min will need to be randomised in the main definitive study to detect a reduction in the mean incidents from 18% to 12%. Our plan in this pilot trial is to investigate whether it is feasible to randomise 60 patients in a period of 6 months in a recruitment rate of 10 patients per month from our centre. This complies with previous recommendation for good practice that pilot randomised control trials should recruit a minimum number of 60 patients [24]. The results from this pilot data will allow us to calculate a more accurate sample size and trial duration and/or the number of recruiting centres that would be required for the main trial.

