16. PLANNED ANALYSES

Intention to treat will be considered as the primary analysis. The clinical and economic impact of intraoperative haemofiltration versus no haemofiltration treatment will be examined. Analysis of the primary endpoint and other continuous data will be performed by using a 2-sided unpaired t-test or an equivalent non-parametric test. Categorical secondary outcome measures will be examined using a Chi-square test or Fisher's exact test as required. The potential cost differences per patient will be estimated with confidence intervals. Exploratory analysis will be undertaken using Bayesian Value of Information methods described by Tan and Smith [25] that balances the benefit of detecting a minimally significant difference with at least a given power against the costs of the patient sample size and/or the risk that the research poses to patients. The result of this analysis will provide guidance on the optimal sample size to use in a future RCT that would seek to evaluate the impact of haemofiltration on healthcare costs.

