1. Reduction in NHS costs by cutting overall ICU treatment costs- Currently, the cost of an intraoperative haemofiltration is approximately £200 a patient which is only 3-4% of what it would cost to perform postoperative continuous veno-venous haemofiltration or dialysis in intensive care units (ICU)/high-dependent units (up to £5000-£6000 a patient over and above standard costs). If the study can establish that intraoperative haemofiltration for patients with renal impairment is effective at reducing the likelihood of postoperative haemofiltration, length of stay in ICU and hospital this will represent an important treatment strategy that could save the NHS millions of pounds every year. Thus there is potential for this study to influence clinical decision making, identify the level of care required to reduce length of stay in ICU and hospital for patients, improve overall operative outcomes and reduce treatment costs.
2. There is also potential for increasing capacity by freeing more ICU beds (wherever the care is carried out) and wards consequently allowing more operations to be performed in the same amount of time.

3. There is also a potential for a reduction in the number of cases that might otherwise go on to develop acute kidney injury, permanent renal damage/ chronic renal failure that would necessitate further long-term use of NHS resources.

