21.2 INFORMING POTENTIAL TRIAL PARTICIPANTS OF POSSIBLE BENEFITS AND KNOWN RISKS

The patient will be given **patient information sheets** and allowed time to study them (at least a day). Potential trial participant will be informed of the potential benefits and known risks at the time when consent is being sought.

21.3 OBTAINING INFORMED CONSENT FROM PARTICIPANTS WHENEVER POSSIBLE OR PROPOSED ACTION WHERE FULLY INFORMED CONSENT IS NOT POSSIBLE

In line with DIRECTIVE 2001/20/EC OF THE EUROPEAN PARLIAMENT of 2001 all research patients are required to provide written informed consent before enrolment in a trial. Potential participants in this study will be no exceptional.

In summary, the research protocol will be approved in advance by our institutional research & development Committee. Before obtaining informed consent, information will be given in a language and at a level of complexity understandable to the patient in both oral and written form by the investigator or designee. Patients will not be coerced or unduly influenced in order for the patient to participate or remain in the trial and will be given ample time and opportunity to inquire about details of the trial and all questions about the trial should be answered to their satisfaction. If the patient is unable to read the consent form, a witness should be present during the entire informed consent discussion process. After the informed consent form is read to and signed by the patient, they must then be given a copy of the signed and dated informed consent form. Patients that decline consent at this stage will not be included in the study and their results will not be used. However, data on the total number deemed eligible for the study and the proportion of these subjects proceeding to randomisation will be documented. Patient will be informed that they may withdraw or discontinue from the study anytime without giving an explanation and that their action will not affect their standard of care. Patient's that die after randomisation will have their data included in the final analysis, unless legal representatives raise objections.

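### The objectives are feasibility objectives, but the designated primary outcome and its planned test are an efficacy comparison that 60 patients cannot support

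*Protocol*

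**What the plan says.** **Purpose.** Protocol section 4 introduces its aims with "In order to overcome these limitations we propose to at first conduct a pilot feasibility study with the following objectives". Three follow: whether 60 patients can be randomised in 6 months, whether the outcome measures are suitable and reliable, and how likely recruitment to a main trial is. Section 5.2 describes the same study as a "pilot randomised clinical trial that will evaluate the efficacy in terms of the reduction in duration of ICU stay" and adds the removal of harmful toxins to what will be evaluated.

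**Outcomes.** Sections 2 and 14 name ICU stay beyond 3 days as primary. The listed secondary outcomes are all clinical or economic. Neither list contains a feasibility quantity, and no toxin or mediator measurement appears in the outcomes or in section 15 on data collection.

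**Analysis.** Section 16 states that "The clinical and economic impact of intraoperative haemofiltration versus no haemofiltration treatment will be examined". It assigns the primary endpoint a two-sided unpaired t-test or a non-parametric equivalent.

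**Claimed benefit.** Section 21.1, item 1, begins a sentence with "If the study can establish that intraoperative haemofiltration for patients with renal impairment is effective" and goes on to say that this study could influence clinical decisions. Section 5.3 has nearly the same paragraph, but there the potential belongs to the main definitive study.

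**Feasibility content.** Section 13 sets the target of 60 patients in 6 months at 10 per month. Section 14 says the outcomes will be judged for suitability and reliability, and that deviation and crossover rates will be reported. Section 21.3 says that "data on the total number deemed eligible for the study and the proportion of these subjects proceeding to randomisation will be documented". Sections 7.3 and 16 plan a Value of Information analysis to size a future trial.

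**The concern.** The primary outcome and its analysis decide what a report leads with. Here they answer a question that section 4 does not ask, and the quantities that section 4 does ask about have no place in either outcome list or in the analysis section. Followed as written, the leading result of the pilot is a p-value for efficacy.

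That p-value is very likely to be non-significant even if the assumed benefit is real, and readers may take it as evidence of no effect. Recruitment, adherence to allocation and data completeness, which the pilot is well placed to estimate, would then be secondary reporting. The wording in section 21.1 adds to this: it forms part of the argument that benefits justify risks, and it credits a 60-patient pilot with a benefit that only the definitive trial could deliver.

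**Working it through.** **Inputs**
- Control rate 18%: section 13, local audit ("surgery in years between 2002 and 2008 were 18" per cent).
- Experimental rate 12%: section 13 ("reduced to at least a mean of 12% because of intraoperative haemofiltration").
- Definitive trial: section 13 ("80% power (2-sided $\alpha=0.05$), 1112 patients with GFR <60 ml/min will need to be randomised in the main definitive study").
- Pilot size 60: sections 2 and 13. I take 30 per arm. The ratio is not stated in words, but section 9 uses blocks of 2, 4 and 6 to balance the groups.
- No dropout, in line with section 12.

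**Step 1: reproduce the protocol's figure.** With pooled variance and no continuity correction, the number per arm is

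n = [1.96·√(2·0.15·0.85) + 0.8416·√(0.18·0.82 + 0.12·0.88)]² / 0.06²
= [1.96·0.5050 + 0.8416·0.5032]² / 0.0036 = 554.8, rounded up to 555.

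The total is 1110, against the stated 1112. The protocol's figure is sound.

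**Step 2: power of the pilot, normal approximation.**
- Standard error under no difference: √(2·0.15·0.85/30) = 0.0922.
- Standard error under 18% and 12%: √(0.2532/30) = 0.0919.
- Power = Φ[(0.06 − 1.96·0.0922)/0.0919] = Φ(−1.31) = 9.4%.

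**Step 3: power by exact enumeration of two binomials, 30 each.**

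| Test | Power |
|---|---|
| Unpaired t-test on the 0/1 outcome | 10.1% |
| Chi-square, uncorrected | 10.1% |
| Fisher's exact, or Yates-corrected chi-square | 4.2% |

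**Step 4: precision.** Expected numbers of long stays are 30·0.18 = 5.4 and 30·0.12 = 3.6. The 95% half-width for the difference is 1.96·0.0919 = 0.180, or 18 percentage points. An observed difference equal to the target of 6 points would have an interval from about −12 to +24 points.

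**Step 5: direction.** With the assumed benefit real, the haemofiltration arm has more long stays than control in 20.0% of such pilots and the same number in 11.8%, which together make 31.8%.

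**Step 6: is feasibility an open question?** Section 5.3 reports up to 90 eligible patients in 2008-2009 and predicts more than 100 in the target year. That is 90/12 = 7.5 per month at most in the earlier year and somewhat above 100/12 = 8.3 in the later one, before any refusals. The target is 10 randomised per month. Recruitment is therefore a result with real uncertainty and direct bearing on the main trial.

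**The case against.** The strongest reply is that the protocol knows it is a pilot. Section 13 says an accurate sample size cannot be set at this stage and puts the definitive trial at 1112, and section 5.3 promises only a preliminary indication. No power is claimed for 60 patients. Section 5.2 is background and section 21.1 a list of potential benefits; neither governs conduct. The 4% figure also uses a test that section 16 assigns to categorical secondary outcomes. All of this is fair. It is why the power figure serves here only to show that the designated test is uninformative, and why 10% is the figure to quote.

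Three stronger readings may tempt a reader, and the protocol does not support them:
- *Every planned analysis is an efficacy or cost comparison.* The Value of Information analysis and the deviation and crossover rates are not.
- *The pilot cannot answer its own objectives.* The first objective has a numerical target in section 13, and section 21.3 documents eligible and randomised counts. Section 14 commits to judging suitability and reliability.
- *Progression to the main trial hangs on the p-value.* No section says so. Section 13 uses the pilot data to set sample size, duration and number of centres.

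Numerical progression thresholds and rules for judging reliability could sit in a statistical analysis plan that is not shown, so their absence is not part of this point. The choice of primary outcome, the named test, the efficacy and toxin aims and the benefit claim are protocol text, and an analysis plan would not remove them.

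**Conclusion.** The point stands in a limited form. The designated primary outcome and the section 16 analysis do not match the section 4 objectives, and sections 5.2 and 21.1 state purposes that conflict with sections 4 and 5.3. The planned test has about 10% power for the protocol's own effect (4% with Fisher's exact test), and the interval is three times as wide on each side as the effect sought (18 against 6 points).

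These figures assume 30 per arm, no dropout, and a test applied to ICU stay beyond 3 days as a yes/no outcome. Section 16 groups the primary endpoint with continuous data; if days of stay were tested instead, power could not be computed from the document. The mismatch itself depends on none of these assumptions. It should be corrected, but the feasibility data are largely being recorded already and the design need not change.

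**What to change.** 1. In sections 2, 14 and 16, make these the primary pilot results, each with a 95% confidence interval: patients randomised per month against the target of 10; proportion of eligible patients randomised; proportion receiving the allocated arm; completeness of the outcome data.
2. Keep ICU stay beyond 3 days as the candidate primary outcome of the main trial. Report it by arm as a difference in proportions with a 95% confidence interval and no significance claim.
3. In section 5.2, delete the statement that the pilot evaluates efficacy, and the toxin-removal aim, which has no outcome behind it.
4. In section 21.1, tie the benefit to a definitive trial, as section 5.3 already does.

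The cost is a protocol amendment, mostly of wording. The counts needed come from the screening, randomisation, crossover and case record data already planned. The pilot gives up an efficacy test that it could not support.
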